3.5.4 Day 6; Treatment Administration

Procedures performed:

- Treatment self-administration by patients

3.5.5 Day 7 (+2 Days); Follow-up Visit

Patients will visit the clinic on Day 7 to have gynecological examination performed. The Investigator or an authorized designee will assess the presence of vulvovaginal signs (erythema, edema, or excoriation) and symptoms (itching, burning, or irritation) and score each sign and symptom.

Vaginal samples will be examined by microscope to reveal yeast forms (hyphae or pseudohyphae) or budding yeast and secretion samples collected by swab to be used for sequencing analysis of the vaginal microbiome. Vaginal pH will also be assessed.

If VVC symptoms are still present, patients will have prolonged treatment and receive additional doses of investigational product to be administered at home on Day(s) 7, 9, 11, and 13.

In addition, patients will be asked questions from the patient questionnaire to assess: usability; concomitant medications; and AEs, if any.

Procedures performed:

- Gynecological examination by Investigator or authorized designee evaluating signs (erythema, edema, or excoriation) and symptoms (itching, burning, or irritation of VVC according to the scoring scale
- Fungal KOH microscope assessment
- Vaginal swab for sequencing
- Vaginal pH
- Recording of:
 - concomitant medications,
 - adverse events, and
 - usability
- Treatment dispensing and self-administration by patients if receiving prolonged treatment

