Name of Products: Gedea Pessary (commercial name pHyp)
Name of Active Ingredient: Glucono-delta-lactone (GDL) and sodium gluconate (NaG)
Title of Study: An open-label study to evaluate clinical performance of Gedea Pessary in adult women with vulvovaginal candidiasis (VVC).
Clinical Investigation Plan Number: QRS-CL1-003
Investigators and Study Center(s): NAME , VO Kvinnosjukvård, Skånes universitetssjukvård, Lund, Sweden NAME , Annerokliniken, Löddeköpinge, Sweden NAME , Hoftekliniken, Helsingborg, Sweden Kliniska prövningssenheten, Kliniska Studier Sverige - Forum Söder, Skånes universitetssjukhus, Lund, Sweden
Classification of Trial: Feasibility Clinical Investigation
Objectives: To investigate the clinical performance, tolerability, and safety of the investigational product.
Methodology: This is an open-label, single-armed, multi-center study to evaluate clinical performance, tolerability, and safety of Gedea Pessary in 24 adult women with VVC. On Day 0, patients will have gynecological examination, vaginal samples taken, and will receive the investigational product to be self-administered 2 days apart (Day[s] 0, 2, 4, and 6). Patients will be examined after 7 days with respect to VVC signs and symptoms and if not cured, will receive prolonged treatment on Day(s) 7, 9, 11, and 13. Patients will be followed-up by telephone up to 29 days after last treatment. Vaginal samples will be used for confirming diagnosis and microbiome analyzes. Patient questionnaires will be used for assessing VVC symptoms, usability, and adverse events (AEs).
Number of Subjects Planned: Twenty-four (24) patients
Diagnosis and Main Criteria for Inclusion: Inclusion Criteria: 
• Adult, post-menarchal, pre-menopausal women aged 18 years or older

- Diagnosis of VVC, defined as having a white or creamy vaginal discharge plus the following findings:
 1. At least 2 of the following signs and symptoms of VVC that are characterized as at least moderate: itching, burning, irritation, edema, redness, or excoriation.
 2. Potassium hydroxide (KOH) or saline preparation from the inflamed vaginal mucosa or secretions revealing yeast forms (hyphae or pseudohyphae) or budding yeasts.
- Having decisional capacity and providing written informed consent
- Negative urine pregnancy test at screening
- Refrain from using any intravaginal products (i.e., contraceptive creams, gels, foams, sponges, lubricants, or tampons, etc.) during the study period

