3 STUDY DESIGN

3.1 General outline

This is an open-label, single-armed, multi-center study to evaluate clinical performance, tolerability, and safety of Gedea Pessary in 24 adult women with VVC. Patients seeking treatment can be screened for study participation. Included patients will have gynecological examination, including collection of CVVS data, vaginal samples taken, and will receive the

Protocol Version 3.0, 24Oct2018

[figure not shown]
LINK Medical Research | Protocol template

Version 2.0 | Effective date 17Apr2018

investigational product to be self-administered at Day(s) 0, 2, 4, and 6. Patients will again be examined after 7 days and CVVS data will be collected. Prolonged treatment at Day(s) 7, 9, 11, and 13 will be given to patients not cured at Day 7; including re-examination at Day 14. Patients will be followed up by telephone up to 29 days after last treatment administration. Vaginal samples will be used for confirming diagnosis and microbiome analyzes. Patient questionnaires will be used for assessing VVC symptoms, usability, and AEs.

Figure 1 Study Flow Chart

Patients not receiving prolonged treatment

VVS = Vulvovaginal Symptoms, VS = Vaginal Swab, CVVS = Composite Vulvovaginal Signs and Symptoms

Patients not receiving prolonged treatment applies to patients cured at Day 7. If not cured, the flow chart *patients receiving prolonged treatment* applies. Patients will here receive fluconazole if not cured at Day 14. Adverse events will be assessed throughout the study

Protocol Version 3.0, 24Oct2018

LINK Medical Research | Protocol template

Version 2.0 | Effective date 17Apr2018

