3.5.3 Day 4 (+2 Days); Follow-up Telephone Contact

On Day 4, patients will self-administer the investigational product and will be contacted by telephone by the Clinical Trial Unit. Telephone contact up to Day 6 will be allowed if Day 4 falls on a weekend. The treatment should nevertheless be self-administered on Day 4. Patients

will be asked questions from the patient questionnaire about: VVC symptoms (itching, burning, or irritation); concomitant medications; and AEs, if any.

Procedures performed:

- Treatment self-administration by patients
- Symptoms of VVC (itching, burning, or irritation) evaluated by patients according to the scoring scale
- Recording of:
 - concomitant medications, and
 - adverse events

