3.5.10 Day 14 (+2 Days); Follow-up Visit

Applicable to patients receiving prolonged treatment

Patients receiving prolonged treatment at Day 7 due to still-present VVC symptoms will visit the site on Day 14 to have gynecological examination performed and vulvovaginal signs (erythema, edema, or excoriation) and symptoms (itching, burning, or irritation) assessed by the Investigator or an authorized designee. Patients will receive fluconazole should symptoms still be present.

Vaginal samples will be examined by microscope to reveal yeast forms (hyphae or pseudohyphae) or budding yeast and secretion samples collected by swab to be used for sequencing analysis of the vaginal microbiome.

In addition, patients will be asked questions from the patient questionnaire to assess usability and AEs, if any.

Procedures performed:

- Gynecological examination by Investigator or authorized designee evaluating signs (erythema, edema, or excoriation) and symptoms (itching, burning, or irritation) of VVC according to the scoring scale
- Fungal KOH microscope assessment
- Vaginal swab for sequencing
- Recording of:
 - concomitant medications,
 - adverse events, and
 - usability

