6 CLINICAL PERFORMANCE

6.1 Clinical Performance Assessments

Assessments described below in [Section 6.1.1](#), gynecological examination, will be used to collect the following 6 vulvovaginal signs and symptoms:

- Vulvovaginal signs of: erythema, edema, and excoriation; and
- Vulvovaginal symptoms of itching, burning, and irritation.

The intensity of each of the signs and symptoms will be scored as:

- 0 = none (absent),
- 1 = mild (slight),
- 2 = moderate (definitely present), or
- 3 = severe (marked, intense).

The scores will be added together and the sum defined as the CVVS score.

A CVVS score equal to or below 3 on Day 7 will be defined as clinical cure, and is a co-primary study endpoint together with safety and tolerability evaluation.

The CVVS score will also be used for the following secondary endpoints:

- Proportion of patients having a reduction in CVVS score on Day 7 compared to Day 0.
- Change in the CVVS score from Day 0 to Day 7.
- Recurrence rate at Day 14 and Day 35, defined as the proportion of patients clinically cured at Day 7 and thereafter responding “yes” to a yes/no question from the patient questionnaire on whether the symptoms have recurred.
- Proportion of patients receiving prolonged treatment.
- Clinical cure rate on Day 14, defined as the absence of signs and symptoms of VVC in terms of having a CVVS score equal to or below 3.
- Proportion of patients having a reduction in CVVS score on Day 14 compared to Day 0.
- Change in the CVVS score from Day 0 to Day 14.
- Recurrence rate at Day 21, and Day 42, defined as the proportion of patients clinically cured at Day 14 and thereafter responding “yes” to a yes/no question from the patient questionnaire on whether the symptoms have recurred.
- Proportion of patients receiving prescription for fluconazole at Day 14.

Assessments described in [Section 6.1.2](#), patient questionnaire, will be used to assess the following secondary endpoints:

- Proportion of patients having a reduction in the sum of the 3 vulvovaginal symptoms scores (itching, burning, and irritation) on Day 4 and Day 7, compared to Day 0.
- Change in the sum of the 3 vulvovaginal symptoms scores (itching, burning, and irritation) from Day 0 to Day 4 and Day 7.
- Usability, measured by patient questionnaire.

- Proportion of patients having a reduction in the sum of the 3 vulvovaginal symptoms scores (itching, burning, and irritation) on Day 11, Day 14, Day 21, and Day 42, compared to Day 0.

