## 4 Study design

This is an open-label, single-armed, multi-center study to evaluate clinical performance, tolerability, and safety of Gedea Pessary in 24 adult women with VVC. Patients seeking treatment can be screened for study participation. Included patients will have gynecological examination, including collection of CVVS data, vaginal samples taken, and will receive the investigational product to be self-administered at Day(s) 0, 2, 4, and 6. Patients will again be examined after 7 days and CVVS data will be collected. Prolonged treatment at Day(s) 7, 9, 11, and 13 will be given to patients not cured at Day 7; including re-examination at Day 14. Patients will be followed up by telephone up to 29 days after last treatment administration. Vaginal samples will be used for confirming diagnosis and microbiome analyzes. Patient questionnaires will be used for assessing VVC symptoms, usability, and AEs.

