## Figure 1 Study Flow Chart

VVS = Vulvovaginal Symptoms, VS = Vaginal Swab, CVVS = Composite Vulvovaginal Signs and Symptoms

**Patients not receiving prolonged treatment** applies to patients cured at Day 7. If not cured, the flow chart **patients receiving prolonged treatment** applies. Patients will here receive fluconazole if not cured at Day 14. Adverse events will be assessed throughout the study

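### The protocol states the trigger for prolonged treatment in two ways (not cured at Day 7, or symptoms still present), and read literally these re-treat different patients

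*Protocol*

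**What the plan says.** Most statements of the rule tie the second course to cure. The synopsis says: "Patients will be examined after 7 days with respect to VVC signs and symptoms and if not cured, will receive prolonged treatment". Protocol 3.1 says that prolonged treatment "will be given to patients not cured at Day 7", and SAP 4 repeats it: "Prolonged treatment at Day(s) 7, 9, 11, and 13 will be given to patients not cured at Day 7". The note to the flow chart, in both documents, agrees. In the SAP it says that the path without prolonged treatment "applies to patients cured at Day 7. If not cured, the flow chart" for prolonged treatment is followed. Cure is a score rule over three signs and three symptoms (protocol 6.1): "A CVVS score equal to or below 3 on Day 7 will be defined as clinical cure".

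The visit instructions use a different trigger. Protocol 3.5.5 (Day 7 visit) says "If VVC symptoms are still present, patients will have prolonged treatment and receive additional doses of investigational product", with no score threshold. Protocol 3.5.10 (Day 14 visit) looks back on the same decision: "Patients receiving prolonged treatment at Day 7 due to still-present VVC symptoms will visit the site on Day 14". In protocol 3.5.3 the same term covers patient-reported items only: "VVC symptoms (itching, burning, or irritation". Protocol 6.1.1 separates signs, which the investigator assesses, from symptoms, which the patient assesses.

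For the analysis, SAP 7.2.1 and 8.9 form the two groups by whether prolonged treatment was actually received. SAP 7.11, which lists changes and clarifications, does not address the trigger.

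**The concern.** The investigator decides on re-treatment at the Day 7 visit, and 3.5.5 is the text that governs that visit. Taken literally, its rule differs from the score rule in both directions. A patient already counted as cured can be re-treated because a mild symptom remains. A patient who is not cured can go without re-treatment because only signs remain.

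Receipt of treatment defines the analysis groups, so this decision settles who is in them. Under the literal symptom rule, three secondary endpoints change meaning most clearly:

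- The proportion prolonged (v) is no longer simply the complement of Day 7 cure.
- The Day 14/35 recurrence group (vii) loses cured patients who had a residual symptom.
- The Day 14 cure rate (viii) takes in patients who were already cured on Day 7, so it no longer measures cure of first-course failures.

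An uncured, signs-only patient who is not re-treated also has only a telephone contact at Day 14 (protocol 3.5.9), so no Day 14 CVVS exists for her.

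**Working it through.** The plan gives no figure on this point. The check is whether the rules can disagree, for whom, and what one such patient does.

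**1. Where the rules disagree.** Six items, each scored 0 to 3, give 4^6 = 4096 score patterns.

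- Total 3 or less: 1 + 6 + 21 + 56 = 84 patterns. Of these, 1 + 3 + 6 + 10 = 20 have all symptoms at 0, leaving 64 with a symptom. These 64 are cured, yet symptoms are present.
- All symptoms at 0: 4^3 = 64 patterns, of which 64 − 20 = 44 total more than 3. These 44 are not cured, yet no symptoms are present.
- The rules agree on the rest: 3968 re-treated by both and 20 by neither.

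Disagreement covers 64 + 44 = 108 patterns. Examples are itching 1 with all else 0 (cured but re-treated), and erythema 2 with edema 2 and no symptoms (not cured, not re-treated). These are counts of possible patterns, not patient frequencies.

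**2. Illustrative group sizes.** Inputs are 24 patients and the assumed 70% cure rate (protocol 9.3, SAP 5.1). 0.70 × 24 = 16.8, taken as 17 cured and n = 7 not cured.

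**3. One cured patient re-treated.**

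- Proportion prolonged: 7/24 = 29.2% becomes 8/24 = 33.3%.
- Cured patients not re-treated: 17 becomes 16.
- Day 14 cure rate, if x of the n uncured patients are cured by then:
  - she is still cured: (x+1)/(n+1) − x/n = (n−x)/(n(n+1));
  - she is not: x/(n+1) − x/n = −x/(n(n+1)).
- The largest absolute shift is 1/(n+1). For n = 7 it is 12.5 points; for assumed n = 4 or 10 it is 20.0 or 9.1 points.

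**4. One signs-only patient not re-treated.** The proportion prolonged falls from 7/24 to 6/24 = 25.0%. Leaving her out of the n shifts the Day 14 cure rate by (n−x)/(n(n−1)) or x/(n(n−1)) in absolute value, according to whether she would have been cured. The largest value is 1/n, or 14.3 points for n = 7.

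**5. Range if every site used the symptom rule.** Let q be the share of Day 7-cured patients who still report a symptom. The documents do not give q. Assume all uncured patients are symptomatic. The prolonged group is then 24 × (0.3 + 0.7q), and the share of it already cured at Day 7 is 0.7q/(0.3 + 0.7q).

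| q (assumed) | Prolonged, of 24 | Already cured at Day 7 |
|---|---|---|
| 0 | 7.2 | 0% |
| 10% | 8.9 | 19% |
| 25% | 11.4 | 37% |
| 50% | 15.6 | 54% |

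**6. Precision for comparison.** The exact 95% interval for an assumed 3 of 7 is 9.9% to 81.6%. One patient changes what the rate means more than how precisely it is known.

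**The case against.** The strongest reply is that the two wordings are one rule. The plan describes a CVVS of 3 or less as absence of signs and symptoms, so symptoms still present can be shorthand for not cured. The cure-based rule appears in the synopsis, protocol 3.1, SAP 4 and both flow-chart notes, and 3.5.5 has each item scored before the decision. Protocol 3.2.1 also uses symptoms loosely, including abnormal discharge. This reading is plausible and stands as a possibility. It does not close the gap. No section states the equivalence, 3.5.5 itself names signs and symptoms separately before deciding on symptoms alone, and 3.2.1 offers Day 14 fluconazole for any remaining symptoms where the flow-chart note says not cured.

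A second reply is that planned output already covers this: item scores are summarised, and patient listings and deviations are presented. That helps in part. A departure from the trigger cannot be called a deviation until it is settled which trigger applies, and no planned table crosses Day 7 cure with receipt.

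Three stronger readings are tempting but unsupported:

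- That sites actually applied different rules. Nothing in the documents shows this.
- That nine of the 14 secondary endpoints (v and vii to xiv) are distorted. All nine involve the same split, but a concrete distortion can be worked out only for v, vii and viii. Membership by receipt is unambiguous, and the binary endpoints carry no hypothesis test (SAP 7.9.2).
- That uncured signs-only patients inflate the recurrence denominator. This holds only if the default denominator of SAP 7.1.1 applies to an endpoint worded around Day 7-cured patients. That is a separate ambiguity.

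**Conclusion.** The concern holds as a conflict between the visit instructions and the design text, with a real consequence if 3.5.5 is followed to the letter. Patients with CVVS 1 to 3 and a residual symptom would be re-treated, and patients with CVVS above 3 from signs alone would not. The Day 7 primary endpoint does not depend on the trigger. The clearest effects are on v, vii and viii; the other prolonged-group endpoints share the group, but no specific effect is shown for them.

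The size cannot be determined from the documents. It is zero if all sites used CVVS above 3, or if no patient fell in either discordant category. The per-patient figures rest on 24 patients, 70% cure and 7 uncured patients. In this small single-arm feasibility study the matter is one of interpreting descriptive secondary results, and it is worth correcting because the correction is cheap.

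**What to change.** **Protocol:** in 3.5.5 and 3.5.10, state that prolonged treatment is given if and only if Day 7 CVVS is above 3. Aligning the Day 14 fluconazole wording in the same way is optional.

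**SAP:**

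- Tabulate Day 7 cure status by receipt of prolonged treatment and by any residual symptom (symptom sum above 0), and list discordant patients. The symptom column is needed because a table without discordant patients fits either rule when no cured patient had a symptom and no uncured patient lacked one.
- Keep the planned analyses. If there are discordant patients, also report the Day 14 cure rate among prolonged patients with Day 7 CVVS above 3.
- In that case also report Day 14/35 recurrence among Day 7-cured patients not re-treated, stating the denominator and how many cured patients were re-treated.

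If enrolment has ended, only the SAP part applies. Protocol 12 planned the last visit for February 2019, and the SAP was final in January 2020.

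**Cost:** two protocol sentences, one table and one listing, all from variables the SAP already presents or derives. The downside is an extra table and, if the restricted rates are needed, small denominators.

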3.5.6 Day 9; Treatment Administration

Applicable to patients receiving prolonged treatment

Procedures performed:

- Treatment self-administration by patients

3.5.7 Day 11 (+2 Days); Follow-up Telephone Contact

Applicable to patients receiving prolonged treatment

Patients receiving prolonged treatment on Day 7 will self-administer the investigational product and will be contacted by the Clinical Trial Unit by telephone on Day 11. Telephone contact up to Day 13 will be allowed if Day 11 falls on a weekend. The treatment should nevertheless be self-administered on Day 11. Patients will be asked questions from the patient questionnaire about: VVC symptoms (itching, burning, or irritation), concomitant medications; and AEs, if any.

Procedures performed:

- Treatment self-administration by patients
- Symptoms of VVC (itching, burning, or irritation) evaluated by patients according to the scoring scale
- Recording of:
 - concomitant medications, and
 - adverse events

3.5.8 Day 13; Treatment Administration

Applicable to patients receiving prolonged treatment

Procedures performed:

- Treatment self-administration by patients

3.5.9 Day 14 (\pm 2 Days); Follow-up Telephone Contact

Applicable to patients NOT receiving prolonged treatment

Patients not receiving additional doses of investigational product on Day 7 will be contacted by the Clinical Trial Unit by telephone on Day 14. Patients will be asked questions from the patient questionnaire about VVC symptoms (itching, burning, or irritation), recurrence, concomitant medications, and AEs, if any.

Procedures performed:

- Vulvovaginal candidiasis recurrence
- Symptoms (itching, burning, or irritation) of VVC evaluated by patients according to the scoring scale
- Recording of:
 - concomitant medications, and
 - adverse events

3.5.10 Day 14 (+2 Days); Follow-up Visit

Applicable to patients receiving prolonged treatment

Patients receiving prolonged treatment at Day 7 due to still-present VVC symptoms will visit the site on Day 14 to have gynecological examination performed and vulvovaginal signs (erythema, edema, or excoriation) and symptoms (itching, burning, or irritation) assessed by the Investigator or an authorized designee. Patients will receive fluconazole should symptoms still be present.

Vaginal samples will be examined by microscope to reveal yeast forms (hyphae or pseudohyphae) or budding yeast and secretion samples collected by swab to be used for sequencing analysis of the vaginal microbiome.

In addition, patients will be asked questions from the patient questionnaire to assess usability and AEs, if any.

Procedures performed:

- Gynecological examination by Investigator or authorized designee evaluating signs (erythema, edema, or excoriation) and symptoms (itching, burning, or irritation) of VVC according to the scoring scale
- Fungal KOH microscope assessment
- Vaginal swab for sequencing
- Recording of:
 - concomitant medications,
 - adverse events, and
 - usability

3.5.11 Day 21 (± 2 Days); Follow-up Telephone Contact

Applicable to patients receiving prolonged treatment

Patients receiving prolonged treatment on Day 7 will be contacted by the Clinical Trial Unit by telephone on Day 21. Patients will be asked questions from the patient questionnaire pertaining to VVC symptoms (itching, burning, or irritation). Questions on concomitant medications, recurrence, and AEs, if any, will also be asked.

Procedures performed:

- Vulvovaginal candidiasis recurrence
- Symptoms (itching, burning, or irritation) of VVC evaluated by patients according to the scoring scale
- Recording of:
 - concomitant medications, and
 - adverse events

